6.1.4.3 Overall radiologic tumor response status after neoadjuvant LDFRT-FOX

The radiologic response status after neoadjuvant LDFRT-FOLFOX is determined by combining the patient’s status including primary rectal tumor, target lymph nodes, and new disease as defined below:

Primary Rectal Tumor & Target Lymph Nodes	New Sites of Disease	Overall Radiographic Tumor Response Status
CR	No	CR
PR	No	PR
SD	No	SD
Not all evaluated	No	Not evaluated
PD	Yes or No	PD

6.2 Clinical tumor evaluation

Baseline and re-evaluation proctoscopy should be performed by the surgeon. The surgeon should perform pre and post treatment examinations. A gastroenterologist may perform proctoscopy in lieu of the surgeon, but then must also perform the follow-up examination. Proctoscopy includes colonoscopy, flexible sigmoidoscopy as well as rigid proctoscopy.

Follow-up proctoscopy should be performed within 3-5 weeks after the completion of LDFRT-FOLFOX.

6.2.1 Guidelines for evaluation of clinically evaluable disease

6.2.1.1 Definition of clinically evaluable disease

To be clinically evaluable, a tumor must be directly visualized at proctoscopy and estimated to have a clinical bidimensional product (BDP) of ≥ 1 cm.

6.2.1.2 Clinical tumor response based on proctoscopy can be classified as the following:

- Complete response (100%)
- Major response (51-100% smaller)
- Moderate response (21-50% smaller)
- Minimal response (0-20% smaller)
- Progression (tumor enlargement)
- Unable to determine

6.2.1.3 Treatment decision after re-evaluation following LDFRT-FOLFOX

- If there is evidence of progressive disease on imaging or clinical assessment, the patient should be referred for standard neoadjuvant chemoradiation off protocol followed by TME.
- If a patient with radiologically measurable disease has an overall imaging tumor response status of stable disease, the patient should be referred for standard neoadjuvant chemoradiation off protocol followed by TME.

- If a patient with disease that is not radiologically measurable has a minimal clinical tumor response, the patient should be referred for standard neoadjuvant chemoradiation off protocol followed by TME.
- Otherwise, the patient should proceed directly to TME.

7.0 SURGERY

Following restaging, patients without evidence of progressive disease, stable disease, or clinical tumor response of 20% or less will undergo a total mesorectal excision (TME) to be performed about 6-8 weeks after completion of LDFRT-FOLFOX. Total mesorectal excision is performed off study as part of standard of care.

Follow up visits will be off protocol and scheduled as per standard of care. Patients will be followed only for survival.

8.0 PATHOLOGICAL TUMOR ASSESSMENT

8.1 Definition of surgical margin status

8.1.1 Margin type

- Proximal: most cephalad portion of the specimen
- Distal: most caudad portion
- Radial: outer circumference of the specimen

8.1.2 Margin positivity

- Positive: tumor \leq 1 mm from any edge of the primary tumor specimen
- Close: tumor >1 but \leq 3 mm from any edge of the primary tumor specimen
- Negative: no tumor within 3 mm from any edge of the primary tumor specimen

8.2 Degree of pathologic treatment response

8.2.1 Pathological complete response (pCR)

A pCR indicates that no gross or microscopic tumor is identified anywhere within the primary tumor specimen or any lymph nodes.

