Low dose fractionated radiation therapy (LDFRT)

Intensity-modulated, bone marrow sparing, whole pelvic radiation therapy
 40 cGy fractions twice per day delivered at least 4–6 hours apart on the first 2 days of each chemotherapy cycle for a total of 6 cycles

	Day 1	Day 2
Oxaliplatin	↓	
Leucovorin	↓	
5-FU	↓	↓
LDFRT	↓↓ (each fraction separated by a minimum of 4 hours)	↓↓(each fraction separated by a minimum of 4 hours)

Primary Objective: To determine whether the addition of concurrent LDFRT to neoadjuvant full dose FOLFOX results in a pCR response rate of at least 35%.

Secondary Objective: To assure that neoadjuvant concurrent LDFRT-FOLFOX maintains a high rate of pelvic R0 resection compared to standard preoperative chemoradiation and total mesorectal excision surgery.

Accrual Goal: 30 patients.

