In addition to surgical advances, significant advances have been made in systemic chemotherapy for patients with colorectal cancer.¹⁸⁻²⁰ Response rates for patients with primary and metastatic colorectal cancer treated with modern chemotherapy regimens such as 5-FU, leucovorin, oxaliplatin (FOLFOX) have routinely exceeded 50% and are frequently as high as 60%-70%.^{19,20} In the context of improved surgical technique, improved chemotherapy, and better radiologic staging, many have questioned whether rectal cancer treatment can be streamlined and/or simplified.

1.1.5 Neoadjuvant FOLFOX chemotherapy without radiation therapy as a potentially new option for locally advanced rectal cancer.

This current protocol builds on work conducted by investigators at the Memorial Sloan-Kettering Cancer Center. In a single-institution trial (MSKCC07-021) that started in March 2007, 32 rectal cancer patients were treated with neoadjuvant FOLFOX chemotherapy instead of standard whole pelvic chemoradiation over 5.5 weeks. Patients also received bevacizumab for the first 4 cycles of therapy. Two patients did

not complete neoadjuvant FOLFOX secondary to cardiac complications likely attributable to bevacizumab. Of the 30 who did complete neoadjuvant treatment, all had R0 resections including TME. Eight of those 30 had pathologic complete responses (pCR) (27%). One patient died postoperatively, and 3 patients experienced a recurrence. All 3 recurrent patients had distant metastasis to the lung. With a mean follow-up of 27 months no study participant had a pelvic recurrence, which is notable since none received pelvic RT. These results were so striking that they have led to an ongoing National Cancer Institute-sponsored phase II/III clinical trial (NCT01515787) evaluating the use of neoadjuvant chemotherapy alone in locally advanced rectal cancer patients who are planned to undergo a low anterior resection with total mesorectal excision. The phase II component of the trial aims to assure that neoadjuvant FOLFOX maintains a high rate of pelvic R0 resection compared to standard pelvic chemoradiation and is also non-inferior with respect to time to local recurrence. The phase III component of the trial aims to compare the pCR rate between neoadjuvant FOLFOX and standard pelvic chemoradiation. Lastly, this trial also will evaluate treatment-related toxicity from each of the respective treatment arms.

[figure not shown]

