2.0 OBJECTIVES

2.1 Primary Objective

To determine whether the addition of concurrent LDFRT to neoadjuvant full dose FOLFOX results in a pCR response rate of at least 35%.

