5.1 Chemotherapy

Neoadjuvant FOLFOX (5-FU + leucovorin + oxaliplatin)

This regimen will be repeated every 2 weeks for 6 cycles; (1 cycle = 14 days).

Given first: Oxaliplatin 85 mg/m^2 IV in D5W 500 mL over 2 hours, Day 1

Given second: Leucovorin 200 mg/m^2 IV bolus in D5W 250 mL over 2 hours, Day 1

Given third: 5-FU 400 mg/m^2 IV bolus in a syringe given over 5–15 minutes, Day 1, then $2,400 \text{ mg/m}^2$ in 240 mL of 0.9% Sodium Chloride via continuous IV infusion over 48 hours, Days 1–2

Note: Oxaliplatin is administered first, prior to leucovorin; alternatively leucovorin may be administered (via separate infusion containers) concurrently with oxaliplatin.

5.1.1 If necessary to accommodate holidays, patient schedule or other justified circumstance approved by the PI, the schedule may be modified by \pm 3 days.

5.1.2 Chemotherapy dose modification is at the discretion of the treating medical oncologist, although any patient who requires dose modification below dose level -2 will be removed from study participation. There are no restrictions on dose modifications for the sixth cycle of FOLFOX.

5.1.3 Patients who cannot tolerate 6 cycles of FOLFOX or those who require dose modification below dose level -2 or those who are found to be ineligible for the study based on central review of either the baseline or the follow up MRI or those that withdraw consent will receive preoperative combined modality chemoradiation with infusional 5-FU. There are no restrictions on dose modifications for the 6th cycle of neoadjuvant FOLFOX.

5.1.4 Patients receiving oxaliplatin on this study should be counseled to avoid cold drinks, chewing ice chips, and exposure to cold water or air because the sensory neurotoxicity often seen with oxaliplatin appears to be exacerbated by exposure to cold. The period of time during which the patient appears to be at risk for these cold-induced sensory neuropathies is not well documented. Patients should exercise caution regarding cold exposure during the treatment period. Peripheral sensory neuropathies can occur at any time after receiving oxaliplatin therapy.

5.1.5 Concurrent medications are at the discretion of the treating physician.
Current Greenebaum [Comprehensive](#) Cancer Center recommended:
Ondansetron 16 mg PO daily, if patient unable to take orally give 8 mg IV.
Dexamethasone 12 mg PO daily, if; unable to take orally give IV.

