12.0 PATIENT DISCONTINUATION

Patients may discontinue study treatment at any time. Any patient who discontinues treatment will be encouraged to return to the study center to undergo treatment discontinuation assessments. The primary reason for discontinuation should be documented.

Reasons for discontinuation of a patient by the investigator include, but are not limited to, the following:

- Documented disease progression or <20% clinical response to LDFRT-FOLFOX
- Symptomatic progression, characterized by increasing tenesmus or hematochezia, decreasing stool caliber, or other signs of imminent bowel obstruction.
- Patient not able or willing to complete the prescribed radiation therapy.
- Patient not able or willing to complete 6 cycles of neoadjuvant FOLFOX.
- Patient non-compliance.
- Patient withdraws consent to participate in the study.
- Persistent (≥ 3 weeks) NCI CTCAE version 4.0 grade 3-4 adverse event or any significant adverse event that compromises the patient's ability to participate in the study.
- Investigator determination that it is not in the patient's best interest to continue participation. It is the right and duty of the Investigator to interrupt the treatment of any subject whose health or well-being may be threatened by continuation in this study. Such subjects should be withdrawn from the study and referred for standard of care treatment.

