14.0 STATISTICS

Our hypothesis is that preoperative concurrent LDFRT and FOLFOX will result in a pCR rate of at least 35%. Thus our power analysis will rely on precision related to estimating the CR rate. Additionally, given that we will use the information from this study to design a prospective experimental study, we seek to enroll 30 patients within 24 months. As such, a sample size of 30 patients produces a two-sided 95% confidence interval with a width equal to 0.36 when the CR rate is 35%.

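### The primary pCR rate has no stated denominator and no rule for scoring patients diverted to off-protocol chemoradiation, so it most naturally falls on selected completers and reads too high

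*Combined protocol and SAP*

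**What the plan says.** The primary objective (section 2.1) asks whether adding LDFRT to FOLFOX "results in a pCR response rate of at least 35" percent. The outcome is defined pathologically in section 8.2.1: "A pCR indicates that no gross or microscopic tumor is identified anywhere within the primary tumor specimen or any lymph nodes". Section 8.2.2 defines non-pCR as a surgical specimen with residual tumor, so a patient with no specimen in the study is in neither class.

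Several sections take patients off the path to that specimen:

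- Section 5.1.2: "any patient who requires dose modification below dose level -2 will be removed from study participation". The sixth cycle carries no dose restriction.
- Section 5.1.3 sends patients who cannot tolerate six cycles, need a dose below level -2, prove ineligible on central MRI review or withdraw consent to preoperative chemoradiation with infusional 5-FU.
- Section 6.2.1.3, for progression, stable disease or minimal clinical response: "the patient should be referred for standard neoadjuvant chemoradiation off protocol followed by TME".
- Section 7.0 describes TME about 6-8 weeks after LDFRT-FOLFOX for the remaining patients. Appendix I places the pathology evaluation in that same window.

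Section 14.0 gives the sample size by precision: "a sample size of 30 patients produces a two-sided 95% confidence interval with a width equal to 0.36", at a rate of 35%. Section 10.1 adds a two-stage rule that stops if 0 of the first 9 respond and rejects the combination if 3 or fewer of 30 respond. Neither section names an analysis set, says what happens to diverted patients in the count, or gives a replacement rule.

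**The concern.** Patients leave the LDFRT-FOLFOX path because they respond poorly or cannot tolerate it. If they drop out of the denominator, the remaining patients are selected on both counts and the pCR rate is biased upward. This is the only primary endpoint of a single-arm trial whose result is meant to inform the design of the next study. If the scoring is not fixed in advance, two analysts following the same text could report materially different rates from the same patients, and the choice could be made with the results in view.

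**Working it through.** **Stated figures first.** The exact (Clopper-Pearson) 95% interval at 10.5/30 = 35% is 0.186 to 0.545, width 0.359, which matches the stated 0.36. The two-stage rule (0 of 9; 3 of 30; null 0.05, alternative 0.25) gives a probability of early termination of 0.630, expected sample size 16.76, type I error 0.049 and power 0.902. All of these agree with section 10.1. The arithmetic is sound provided all 30 patients count.

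**Inputs for the bias check**

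- *b*: pCR on LDFRT-FOLFOX alone, over all patients who start. Taken as 27%, the pilot figure in section 1.1.5.
- *f*: share diverted. The documents give no rate, so 10%, 20% and 30% are assumptions.
- *q*: pCR after standard chemoradiation, 8% and 15% in the two randomized trials described in section 1.1. Those patients had no prior FOLFOX, so *q* is illustrative.

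**Formulas.** Rate over completers = b/(1 − f). Rate if every specimen counts, including those after chemoradiation = b + f·q.

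| Diverted (f) | All starters | Completers | Every specimen |
|---|---|---|---|
| 10% | 27% | 0.27/0.90 = 30.0% | 27.8-28.5% |
| 20% | 27% | 0.27/0.80 = 33.8% | 28.6-30.0% |
| 30% | 27% | 0.27/0.70 = 38.6% | 29.4-31.5% |

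**In whole patients.** Ten pCRs are 10/30 = 33.3% of starters but 10/28 = 35.7% of completers if two are diverted. Nine pCRs are 9/30 = 30.0% (95% CI 14.7-49.4) but 9/24 = 37.5% (18.8-59.4) if six are diverted.

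**Precision.** With 24 patients the exact width is 0.397 at 8/24 and 0.406 at 9/24, so about 0.40 instead of 0.36.

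**Less likely reading: later specimens are counted.** The chance of at least one miscredited pCR among *m* switched patients is 1 − (1 − q)^m.

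- m = 2: 1 − 0.92² = 15%; 1 − 0.85² = 28%.
- m = 6: 1 − 0.92⁶ = 39%; 1 − 0.85⁶ = 62%.

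At the 5% null with f = 10%, the apparent rate becomes 0.058 to 0.065, and the two-stage type I error rises from 0.049 to between 0.076 and 0.104.

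**Benchmark.** Section 1.1.5 reports 32 treated and two who did not complete, then: "Of the 30 who did complete neoadjuvant treatment, all had R0 resections including TME". The 27% is 8/30. Over all treated it is 8/32 = 25.0%, if both non-completers are scored as non-pCR.

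**The case against.** The strongest reply is that the text, read in sequence, already points to the right analysis. Section 10.1 speaks of treating 9 patients and then studying 30 in total, and section 14.0 uses 30. That could be read as responders over all treated, which is the remedy sought here. It is a possible reading, but no section adopts it, and section 8.2.2 works against it by requiring a specimen before a patient can be a non-pCR.

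A reader might infer that pCRs produced by later chemoradiation will routinely be credited to LDFRT-FOLFOX. The documents do not support that as the natural reading. Section 7.0 and Appendix I put TME and its pathology at 6-8 weeks. On the timeline in section 1.1.3, chemoradiation plus recovery takes 5.5 + 4 to 6 = 9.5 to 11.5 weeks; after restaging at 3-5 weeks, TME comes at about 12.5 to 16.5 weeks. Sections 6.0 and 6.2.1.3 also place that treatment outside the study. What stands is only that section 8.2.1 does not exclude such a specimen.

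A reader might also infer that all data on patients who stop are lost. That is too strong. Section 12.0 encourages discontinuation assessments, section 7.0 keeps survival follow-up, and section 10.3 requires all adverse events to be reported. Removal under section 5.1.2 covers only doses below level -2. The sentence "Such subjects should be withdrawn from the study and referred for standard of care treatment" belongs to the last item in section 12.0, on the investigator's judgment of the patient's best interest; it is not a general rule for toxicity.

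Finally, crossing 35% triggers no formal decision. Section 14.0 contains no test at 35%, both intervals shown for nine pCRs include 35%, and nine responders pass the more-than-3 rule whatever the denominator. This is correct: the harm is a biased estimate, not a reversed test.

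**Conclusion.** The concern holds in this form. The protocol diverts patients because of intolerance or poor response, defines both pCR and non-pCR by a specimen, and never scores those diverted. The most natural result is a completers-only rate that is biased upward.

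With an assumed 10% to 30% diverted and a true rate of 27%, the overstatement is 3.0 to 11.6 percentage points. The only non-completion figure in the documents is 2 of 32 in the pilot. That regimen included bevacizumab, and the figure does not count diversions at restaging, so it does not settle the share here. Even two diverted patients move ten pCRs from below 35% to above it.

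Crediting pCRs after chemoradiation is a secondary risk, and its size rests on rates from a different setting. The 25% benchmark rests on an assumption too, because the pathology of the two pilot non-completers is not reported. The design calculations are correct and need no change.

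**What to change.** In section 14.0, and with the same meaning of *respond* in section 10.1, define the primary outcome as pCR at TME after LDFRT-FOLFOX with no intervening chemoradiation, over all patients who start protocol treatment. Patients who are switched, not resected or without pathology count as non-pCR. Report pCR after off-protocol chemoradiation separately. Leave section 8.2.1 as the pathology definition.

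Reconcile sections 5.1.2, 5.1.3, 6.0, 11.2 and 12.0, which describe stopping and what follows in different terms. Stopping protocol treatment should not end collection of routine toxicity, pathology and survival data unless the patient withdraws consent for data. This concerns data collection only; which treatment follows is for the clinical authors to reconcile.

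When comparing on this basis, state that the 27% benchmark is 8/30 completers, or 25% (8/32) if both non-completers are counted as non-pCR.

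The rule should be in place before results are known. It keeps the sample size at 30, the interval width at 0.36 at a 35% rate, and the two-stage type I error (0.049) and power (0.902). The cost is abstraction of standard-of-care pathology reports and a reported pCR rate that may be slightly lower.

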8.2.2 Pathologic response other than a pCR

The definition of a non-pCR will include any surgical specimen that has any evidence of residual tumor manifest in the primary or regional lymph nodes.

For patients who do not meet criteria for a pCR, the extent of response to pre-operative therapy will be graded using the Tumor Regression Grade (TRG) schema that is included in the AJCC 7th edition. This was also used by Rodel in the pre/postoperative rectal cancer study and was subsequently adopted by the AJCC [Rodel (JCO 2005; 23:8688-8696)]. This schema evaluates the

degree to which the primary rectal tumor specimen has responded to neoadjuvant treatment.

Tumor regression grade (TRG)	Response categorization	Description
TRG 0	Complete	No viable cancer cells
TRG 1	Moderate	Single cells or small groups of cancer cells
TRG 2	Minimal	Residual cancer outgrown by fibrosis
TRG 3	Poor	Minimal or no tumor kill; extensive residual cancer

9.0 ADJUVANT THERAPY

Adjuvant therapy will be prescribed at the discretion of the treating physician(s). Although not required by this protocol, patients with close or positive margins or other features felt by the treating physician(s) to be high risk factors for locoregional recurrence are recommended to receive standard adjuvant chemoradiation.

10.0 DATA SAFETY MONITORING AND ADVERSE EVENT (AE) MONITORING AND REPORTING

10.1 Data and Safety Monitoring / Quality Assurance Committee

This study will be governed by the UMGCC Data Safety Monitoring / Quality Assurance Committee (DSMQAC). The study will be sent to the DSMQAC for a mandatory interim review after the first 6 patients have been accrued. Once the DSMQAC has reviewed and approved the initial 6 patients on the study, 24 additional patients will be enrolled. The study will be reviewed by the DSMQAC on an annual basis and a report will be uploaded in the continuing review submitted to the Institutional Review Board (IRB).

On the basis of an optimal two-stage design to test the null hypothesis that $P \leq 0.05$ (poor pCR response rate) versus the alternative that $P > 0.25$ (UMGCC DSMQAC committee feels that 25% response rate is a reasonable threshold) has an expected sample size of 16.76 and a probability of early termination of 0.63. If preoperative concurrent LDFRT and FOLFOX is actually not effective, there is a 0.05 probability of concluding that it is. If the treatment combination is actually effective, there is a 0.10 probability of concluding that it is not. After treating 9 patients in the first stage, the study will be terminated if 0 respond. If the trial goes on to the second stage, a total of 30 patients will be studied. If the total number responding is less than or equal to 3, the treatment combination will be rejected.

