5.0 TREATMENT PLAN

Treatment must begin within 14 days of registration.

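### Does releasing 24 more patients after the 6-patient committee review undercut the 0-of-9 stop and the expected sample size of 16.76?

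*Combined protocol and SAP*

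**What the plan says.** Section 10.1 has two consecutive paragraphs on enrolment. The first requires a committee (DSMQAC) review once 6 patients have been accrued and continues: "Once the DSMQAC has reviewed and approved the initial 6 patients on the study, 24 additional patients will be enrolled". The second describes an optimal two-stage design for a null pCR rate of 5% against 25%, which "has an expected sample size of 16.76 and a probability of early termination of 0.63". Its rule is: "After treating 9 patients in the first stage, the study will be terminated if 0 respond". It then adds: "If the trial goes on to the second stage, a total of 30 patients will be studied". The combination is rejected if 3 or fewer of the 30 respond.

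Three other sections fix how long the endpoint takes. Section 5.0: "Treatment must begin within 14 days of registration". Section 5.1: "This regimen will be repeated every 2 weeks for 6 cycles; (1 cycle = 14 days". Section 7.0 places the operation, from which pCR is read, "to be performed about 6-8 weeks after completion of LDFRT-FOLFOX". Patients with progression, stable disease or minimal response leave earlier: under section 6.2.1.3, "the patient should be referred for standard neoadjuvant chemoradiation off protocol followed by TME".

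Planned accrual appears twice: 15 months in section 10.2, and 30 patients within 24 months in section 14.0. Section 14.0 does not mention the two-stage rule.

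**The concern.** The two paragraphs do not refer to each other. The first, taken literally, releases the whole remaining sample on committee approval of 6 patients. The second makes patients 10 to 30 depend on at least one pCR among 9. The plan does not say what the 6-patient review assesses, who looks at the stage 1 pCR results, or whether patient 10 may enter while those results are pending. The endpoint is slow, so several patients could enter in that interval.

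Two things would be at stake. If the release displaced the stop, the rule would become 4 or more responses in 30 with no early look. Alpha would then be 0.061 instead of 0.049, and 30 patients would always be enrolled. If a 0/6 look were used in place of 0/9, power at 25% would fall to 0.805. Even with the stop respected, 16.76 equals the number enrolled only if nobody enters between the ninth patient and the stage 1 result.

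**Working it through.** **1. The plan's own figures.** Inputs from section 10.1: n1 = 9, stop at 0; n = 30, reject the regimen at 3 or fewer; p0 = 0.05, p1 = 0.25.

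- Probability of early termination (PET) at p0 = 0.95^9 = 0.6302 (stated 0.63).
- Expected N at p0 = 9 + (1 − 0.6302) × 21 = 16.76 (stated 16.76).
- Probability of declaring activity = Σ over x = 1 to 9 of P(X1 = x) × P(X2 ≥ 4 − x), with X1 ~ Bin(9, p) and X2 ~ Bin(21, p). This gives 0.0489 at p = 0.05 and 0.9019 at p = 0.25, against stated errors of 0.05 and 0.10.

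A search over two-stage designs meeting these error limits also returns 0/9, 3/30 as the one with the smallest expected N.

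**2. Do the two paragraphs conflict?** Their totals agree: 6 + 24 = 30 and 9 + 21 = 30. At uniform accrual, the sixth patient is registered 5/2 = 2.5 to 5/1.25 = 4.0 months after the first. The pCR lag in step 3 is 4.1 to 5.1 months, or about 3.75 months at the shortest if counted from the last dose. When the sixth patient is accrued, therefore, at most the first could have a pCR result. The 6-patient review makes sense as a safety and quality check, not as a pCR look.

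**3. Enrolment if accrual is not paused.** Lag from registration to pCR = (0 to 2) + 6 × 2 + (6 to 8) = 18 to 22 weeks = 4.14 to 5.06 months. Accrual = 30/24 = 1.25 or 30/15 = 2 per month. Overrun = rate × lag.

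Expected enrolment = PET × (9 + overrun) + (1 − PET) × 30 = 16.76 + 0.6302 × overrun.

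| Rate per month | Overrun | Expected enrolment at p = 0.05 |
|---|---|---|
| 1.25 | 5.2 to 6.3 | 20.0 to 20.8 |
| 2 | 8.3 to 10.1 | 22.0 to 23.1 |

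Sensitivity to the lag:

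- Ninth patient leaves at restaging and is counted as a non-response then, (0 to 2) + 12 + (3 to 5) = 15 to 19 weeks: overrun 4.3 to 8.7, expected enrolment 19.5 to 22.3.
- Completion counted from the last dose in cycle 6 (about 10.3 weeks from start), giving 16.3 to 20.3 weeks: 19.7 to 22.7.
- The 9 months that section 10.2 allows for the last patient, taken as the lag: 23.9 to 28.1.

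**4. Effect on the error rates.** None. If the first 9 yield no pCR, the trial stops whatever the overrun patients show. If they yield at least one, the overrun patients are simply part of the 21 in stage 2. The set of outcomes that leads to a positive conclusion is the same.

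**5. Expected excess patients by true pCR rate.** (1 − p)^9 × (5.2 to 10.1):

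| True pCR rate | P(0/9) | Expected excess |
|---|---|---|
| 5% | 0.630 | 3.3 to 6.4 |
| 15% | 0.232 | 1.2 to 2.3 |
| 25% | 0.075 | 0.4 to 0.8 |
| 27% | 0.059 | 0.3 to 0.6 |
| 35% | 0.021 | 0.1 to 0.2 |

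The 15% is the chemoradiation result of the second randomised trial in section 1.1, 27% the FOLFOX result in section 1.1.5, and 35% the target in section 2.1.

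**The case for a change.** The strongest case for a change is that stage 1 exists to limit exposure when the regimen is inactive, and the protocol itself chose 5% as that case and advertises a 0.63 chance of stopping there. An implied gate beside an explicit release is ambiguous. Even a team that respects the gate is not told whether patient 10 may enter while results are pending. If the regimen is inactive and 0/9 occurs, about 5 to 10 further patients would have been enrolled, when section 3.1.8 says each would otherwise have been recommended standard chemoradiation. The remedy would be one paragraph.

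Much of this is factually right. No section links the two rules or mentions a pause, and without a pause expected enrolment at 5% exceeds 16.76 in every scenario tried. What does not follow is that the plan must change:

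- **Linking the release to the stop.** This restates a rule that already binds. A terminated study enrols nobody.
- **Describing the 6-patient review.** This adds detail but alters no result.
- **Holding accrual at 9.** This secures 16.76, but costs up to 18 to 22 weeks (less if a pCR appears early) out of 15 planned months of accrual, and would mean revising the timeline in section 10.2.
- **Restating the expected sample size.** This swaps a correct conventional figure for one that runs from 19.5 to 28.1 depending on the lag and accrual assumed, and it affects no decision.

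The saving is also not lost without a pause. Against a fixed 30, the design saves 30 − 16.76 = 13.2 patients at p = 0.05. With overrun of 5.2 to 10.1 it still saves 30 − 23.1 = 6.9 to 30 − 20.0 = 10.0.

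**Conclusion.** The concern does not call for a change. The termination rule and the conditional second stage stand in the paragraph directly after the release sentence. A team following section 10.1 as a whole would run both: a 6-patient safety and quality review, then the 0/9 rule on the first 9. Early termination of 0.63, expected N of 16.76, alpha of 0.049 and power of 0.902 are all correct, and 16.76 is what it claims to be, the expected sample size of the two-stage design.

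Whether to pause at 9 is left open, and either answer is defensible. Without a pause, expected enrolment at a 5% pCR rate is about 19.5 to 23. That is illustrative only: it assumes uniform accrual of 1.25 to 2 per month, no hold at the 6-patient review, 15 to 22 weeks to outcome, and a stop as soon as the ninth result is known. At 25% or above, the expected excess is below one patient. The conclusion rests on the 0/9 rule being applied to the first 9 patients whatever later patients show, which is what the plan says.
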